1.3 Schedule of Activities (SoA)

TABLE 1: SCHEDULE OF ACTIVITIES: INTERVENTIONAL SUBJECTS

Study Procedure:	Screening ≤14 days prior to Day 0	Day 0 : Begin TMZ Treatment	Week 4 (-3/+7 days) and every 4 weeks until treatment stop	Week 8 (±7 days) and every 8 weeks only until treatment stop	Progression	After Treatment Stop (Week 4 (+/- 7 days) from end of treatment)	Survival follow-up
Informed Consent	X						
Medical History, Demographics	X						
Medication History	X						
MGMT methylation status	X						
Tumor Tissue Sample ⁹	X				X		
MRI of the brain ¹	X			X	X		
Physical Exam	X		X		X	X	
Neurological status, KPS	X		X		X	X	
CBC w/diff	X ¹⁰		X		X	X	
Pregnancy test (urine or serum)	X ¹⁰						
Biochemistry Panel ⁶	X ¹⁰		X		X	X	
Record Steroid Dose	X		X		X		
Quality of Life Questionnaires ²	X			X	X		
RANO	X			X	X		
Temozolomide Cycle		X ⁷	X ⁸				

Study Procedure:	Screening ≤14 days prior to Day 0	Day 0 : Begin TMZ Treatment	Week 4 (-3/+7 days) and every 4 weeks until treatment stop	Week 8 (±7 days) and every 8 weeks only until treatment stop	Progression	After Treatment Stop (Week 4 (+/- 7 days) from end of treatment)	Survival follow-up
Optune Therapy ⁴		X	X		X		
Optune Compliance ⁴			X				
Adverse Events		X	X	X	X	X	
Concomitant Medications		X	X	X	X	X	
Telephone Interview							X ⁵
DICOM Images shipped for electric fields mapping ¹¹		X			X		X

1) Screening MRI should be done within 21 days of study treatment start. MRI of the brain will be performed routinely at baseline and again every 8 weeks +/- 7 days until treatment termination or second progression, whichever is first. An MRI of the head will be obtained within 21 days in the event of clinical signs of progression. After the post-treatment follow up visit and the patient has not progressed by treatment termination, patient will have contrast-enhanced brain MRI every 3 +/- 1 months for 12 months, then every 6 +/- 2 months for 24 months, then yearly +/- 1 month thereafter or until disease progression, whichever comes first. All MRI scans should be performed with and without contrast and include the scalp.
							

2) Quality of Life will be measured using the EORTC QLQ-C30/BN20 and MMSE every 8 weeks +/- 7 days for the first 2 years then every 3 months thereafter.
							

3) Screening visit should occur within 14 days of adjuvant temozolomide start, with the exception of MRI which can be within 21 days (3 weeks) of adjuvant temozolomide start.
							

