
4) Optune therapy should start within two weeks of start of adjuvant temozolomide, but not more than 7 weeks from the end of temozolomide/RT and will be continuous throughout study. Compliance documentation will be obtained every 4 weeks +/- 7 days.
							

5) Every 3 months until death. The only data required during survival follow-up is DOD.
							

6) Biochemistry panel will include electrolytes, creatinine, bilirubin, liver enzymes.
							

7) Patients will begin treatment with temozolomide at 4 weeks (+14 days) from end of radiotherapy. Cycle 1 will be dosed at 150mg/m² daily for 5 consecutive days of a 28-day cycle.
							

Study Procedure:	Screening ≤14 days prior to Day 0	Day 0 : Begin TMZ Treatment	Week 4 (-3/+7 days) and every 4 weeks until treatment stop	Week 8 (±7 days) and every 8 weeks only until treatment stop	Progression	After Treatment Stop (Week 4 (+/- 7 days) from end of treatment)	Survival follow-up

8) Patients will begin treatment with temozolomide Cycle 2 and subsequent cycles every 4 weeks (-3/+7 days) at 200mg/m² PO daily for 5 consecutive days, if CTC hematologic toxicity for cycle 1 is grade < 1 and the CTC non-hematologic toxicity for cycle 1 is grade ≤ 2. If dose escalation is not appropriate, the dose should remain at 150 mg/m² PO daily for 5 consecutive days for Cycle 2 and onward.
							

9) Verification of tissue availability and location should be determined at screening visit. When available, formalin fixed and paraffin embedded (FFPE), pathology slides and/or frozen samples will be obtained for primary tumors and first recurrent tumors.
							

10) Labs to be completed within 3 days for pre-TMZ cycles. Screening and other labs are within the visit windows noted. Pregnancy Test required for WOCBP only at Screening.
							

11) DICOM images will be shipped to Beth Israel Deaconess Medical Center for electric field mapping analysis at baseline, first progression and second progression. Imaging performed between shipping time points should be included in the next shipment.
							

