6.1.1.2 Periodic Evaluation until Treatment Termination

Patients will be seen and examined before each cycle of temozolomide. After a maximum of 12 cycles of adjuvant temozolomide, patients will be seen every 8 weeks. Brain MRI and QoL assessments will be performed every 8 weeks following the baseline MRI for the first 2 years then every 3 months thereafter until second progression (when TTFIELDS treatment will be terminated).

Patients will undergo the following studies or review every month until treatment termination:

- Physical examination
- Neurological status and performance status (KPS)
- Blood exams
- Optune Compliance
- Record of Adverse Events, concomitant medications and steroid dose

Patients will undergo the following studies or review every 8 weeks +/- 7 days until treatment termination:

- Quality of Life Questionnaires (EORTC QLQ-C30/BN20, and MMSE)
- Contrast-enhanced MRI

Screening MRI should be done within 21 days of study treatment start. MRI of the brain will be performed routinely at baseline and again every 8 weeks +/- 7 days until treatment termination or second progression, whichever is first. In case of clinical progression, an MRI will be performed within 21 days.

All MRI scans should be performed with and without contrast.

The data collection for patients who remain on Optune (on-study treatment) and begin 2nd line therapy should include labs and visits adjusted as appropriate for the standard care of that patient's 2nd line therapy.

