8 STUDY ASSESSMENTS AND PROCEDURES

8.1 Efficacy Assessments

8.1.1 Day 0 – Start of TMZ Treatment Cycle 1

- Patients will begin treatment with temozolomide at 4 weeks (+14 days) from end of radiotherapy.
- Cycle 1 will be dosed at 150mg/m² daily for 5 consecutive days of a 28-day cycle.
- Optune therapy should start within two weeks of start of adjuvant temozolomide, but not more than 7 weeks from the end of temozolomide/RT and will be continuous throughout study.
- Review Concomitant Medications
- Update Adverse Events

8.1.2 Week 4 (-3/+7 days) - Start of Subsequent TMZ Treatment Cycles, repeat every 4 weeks up to 12 cycles

- Physical Exam
- Patients will begin treatment with temozolomide cycle 2 and subsequent cycles every 4 weeks (-3/+7 days) at 200 mg/m², if the CTC non-hematologic toxicity for Cycle 1 is Grade ≤2 (except for alopecia, nausea and vomiting), absolute neutrophil count (ANC) is ≥ 1.5 x 10⁹/L, and the platelet count is ≥ 100 x 10⁹/L.
 - The dose remains at 200 mg/m² per day for the first 5 days of each subsequent cycle unless toxicity occurs. If the dose was not escalated at Cycle 2, escalation should not be done in subsequent cycles.
- Neurological status and KPS
- CBC with differential
- Biochemistry Panel (electrolytes, creatinine, bilirubin, liver enzymes)
- Steroid Dose (recorded)
- Optune therapy will be continuous throughout study. Compliance documentation will be obtained every 4 weeks (-3/+ 7 days).
- Review Concomitant Medications
- Update Adverse Events

8.1.3 Week 8 (+/- 1 week) – repeat MRIs every 8 weeks only, until treatment stop

- Contrast-enhanced MRI of the brain
- Quality of life questionnaires (EORTC QLQ-C30/BN20, and MMSE)
- RANO assessment
- Review Concomitant Medications
- Update Adverse Events

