8.1.4 Progression

If progression is identified, the following procedures should be performed:

- Contrast-enhanced MRI of the brain
- Physical Exam
- Neurological status and KPS
- CBC with differential
- Steroid Dose (recorded)
- Biochemistry panel (Electrolytes, creatinine, bilirubin, liver enzymes)
- Quality of life questionnaires (EORTC QLQ-C30/BN20, and MMSE)
- RANO assessment
- Optune Therapy – confirm continuation (See Recommendations for Use of Optune)
- Optune Compliance
- Review Concomitant Medications
- Update Adverse Events
- Tumor Tissue sample – determining availability of FFPE, pathology slides and/or frozen sample(s) for first recurrence

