8.2.1 After Treatment Stop

Week 4 (+/- 7 days) from treatment stop

The following will be performed 4 weeks (+/- 7 days) from treatment stop:

- Physical exam
- Neurological status and KPS
- CBC with differential
- Biochemistry Panel (electrolytes, creatinine, bilirubin, liver enzymes)
- Review Concomitant Medications
- Update Adverse Events

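### The plan gives three different end points for EORTC QLQ-C30/BN20 and MMSE collection; under the visit lists the routine scores stop with treatment although the patient stays on study

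*Combined protocol and SAP*

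**What the plan says.** Quality of life is a secondary endpoint, measured by KPS, EORTC QLQ-C30/BN20 and MMSE (section 3, Table 2). The plan schedules the two questionnaire instruments in several places:

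- **Until treatment stop.** The list in section 6.1.1.2 opens "Patients will undergo the following studies or review every 8 weeks +/- 7 days until treatment termination". In Table 1 (section 1.3) the routine questionnaire mark sits in the column "Week 8 (±7 days) and every 8 weeks only until treatment stop". Section 8.1.3, which also lists the questionnaires, is headed "repeat MRIs every 8 weeks only, until treatment stop".
- **Until second progression.** The opening paragraph of section 6.1.1.2 sets MRI and questionnaires every 8 weeks "for the first 2 years then every 3 months thereafter until second progression (when TTFIELDS treatment will be terminated").
- **By calendar, no end stated.** Footnote 2 of Table 1 has both instruments "every 8 weeks +/- 7 days for the first 2 years then every 3 months thereafter".
- **At progression.** Table 1 marks the questionnaires in the Progression column. Section 8.1.4 includes them under "If progression is identified, the following procedures should be performed", without requiring that the patient still be on treatment.
- **After treatment.** Section 8.2.1 opens "The following will be performed 4 weeks (+/- 7 days) from treatment stop" and lists KPS but neither questionnaire; section 6.1.1.3.2.6 does not list them either. Footnote 5 of Table 1 says of the stage that follows: "The only data required during survival follow-up is DOD".

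Sections 6.1.1.3.1.1, 6.1.2.6 and 6.1.2.6.1 end Optune at 24 months at the latest. Section 6.1.2.6.1 also stops it for SAEs probably or definitely related to TTFields, for prohibitive clinical or functional deterioration, and at second progression. Section 7.1 keeps patients who have stopped treatment on study.

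**The concern.** Sites cannot follow all of these rules at once, so the data collected will depend on which part of the protocol a coordinator works from. The visit lists are what a site is most likely to use, and they end the routine questionnaires with treatment. The post-stop visit then passes without them even though the patient is in clinic and KPS is recorded.

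Some reasons for stopping the device are themselves tied to quality of life. If scores are lost mainly in patients who stopped for those reasons, later on-treatment averages describe a selected group, and the burden of treatment may look lighter than it was. Patient-reported scores not taken at the time cannot be recovered from charts. Section 10 has no quality-of-life analysis and no missing-data rule that would limit the problem.

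**Working it through.** The plan states no quality-of-life sample size, effect or analysis, so there is no figure to reproduce. The check compares the schedules and then sizes what is at stake. Treatment stop is taken to mean the end of Optune, because section 6.1.1.2 continues 8-weekly visits after temozolomide ends.

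**1. Can the rules be reconciled as written?** Footnote 2 and the 6.1.1.2 narrative both foresee 3-monthly assessments after year 2. With Optune ending by month 24, a rule that stops at treatment stop gives no routine assessment after that date. Section 6.1.1.2 therefore contradicts itself as well as footnote 2.

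**2. Scheduled routine assessments, patient stopping Optune at month 4 (about week 17) and alive at week 104**

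| Rule | Routine post-baseline assessments |
|---|---|
| Visit lists | weeks 8 and 16 = 2, plus any Progression visit |
| Footnote 2, read as independent of treatment | 104 / 8 = 13 |

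From month 24 to month 60 the calendar rule adds at most (60 - 24) / 3 = 12. That maximum applies only to the earliest enrolled: with 36 months of accrual in a 60-month study, the last patient enrolled has 60 - 36 = 24 months.

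**3. How many patients reach month 24?** Section 10 assumes a 22-month control median, improvements of 4 to 8 months, and a Weibull shape k of 2.0 or 1.8. With S(24) = exp(-ln 2 × (24/median)^k):

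| Median (months) | k = 2.0 | k = 1.8 |
|---|---|---|
| 22 | 0.438 | 0.445 |
| 26 | 0.554 | 0.549 |
| 28 | 0.601 | 0.591 |
| 30 | 0.642 | 0.629 |

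On the plan's own assumptions, about 44% to 64% of patients would be alive at month 24, when the conflict applies to all of them.

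**4. Possible distortion of an on-treatment mean.** Let f be the share of living patients off treatment and d their mean deficit. The mean over all living patients is (1 - f) × m + f × (m - d) = m - f × d, where m is the on-treatment mean. The on-treatment mean is therefore too high by f × d. Neither input is in the documents. Assuming f from 0.10 to 0.40 and d from 0 to 15 points on a 0-100 scale:

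- d = 0: 0 points at any f
- f = 0.20, d = 10: 2.0 points
- f = 0.40, d = 15: 6.0 points

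**The case against.** A reader might infer that quality of life would come only from patients still tolerating the device, and that a month-4 stopper contributes nothing more. The documents do not support that. The questionnaires are also taken at screening and at progression, treatment may run past first progression, and KPS is taken 4 weeks after stop. Under section 6.1.1.3.2.6 a patient who has not progressed continues MRI until progression, which triggers section 8.1.4. Clinical deterioration due to the tumour can itself count as progression (section 6.1.1.3.1, Tables 3 and 4). This stands, with one limit: section 6.1.2.6 sends patients removed early for toxicity or progression to one visit and then telephone contact, so the path back to a Progression visit is itself unclear.

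A reader might also infer that the quality-of-life result is biased upward. That is plausible but not shown. No analysis is specified. Direction and size depend on the estimand, on how deaths and missing forms are handled, and on why patients stopped. Stopping at the 24-month cap also ends collection for patients who tolerate the device well, and is not informative in the same way.

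Footnote 2 states a frequency, not an end. Its later period may be on-treatment wording never aligned with the cap: section 6.1.2.5 continues TTFields to second progression without repeating the 24 months. A full off-treatment series is thus one reading of footnote 2, not its stated content. Those treatment-duration passages also need to be reconciled.

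Finally, the objective compares with controls, and section 9.5 collects neither EORTC nor MMSE from controls. That is a separate and more basic gap, which more post-stop scores would not close. It does not remove this point: if the control scores are absent, the scores within the treated arm are the main usable questionnaire evidence.

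**Conclusion.** The conflict is certain from the text. Collection ends at treatment stop, at second progression, or at no stated time, depending on where one reads. Under the visit lists, an early stopper gives no further routine EORTC or MMSE scores except at a Progression visit, while remaining on study and attending a clinic visit where KPS is done.

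The missing scores are probably not missing at random, because related SAEs and deterioration are among the stop reasons. A summary of on-treatment scores would probably be too favourable. The 0 to 6 points illustrate assumed inputs and are not an estimate: the documents give neither a stopping rate nor a score deficit. The primary endpoint is unaffected. The change should be made because it is cheap and the loss is irreversible.

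**What to change.** 1. Choose one rule that continues EORTC QLQ-C30/BN20 and MMSE after treatment stop, and state its end point identically in Table 1, footnote 2, and sections 6.1.1.2 and 8.1.3. Remove the treatment-stop limit for these instruments in 6.1.1.2 and 8.1.3.
2. Add both instruments to the After Treatment Stop visit (Table 1, 6.1.1.3.2.6, 8.2.1).
3. Add them to the existing post-treatment MRI visits for patients who have not progressed, at those visits' own intervals (3-monthly for 12 months, then 6-monthly). Reconcile sections 6.1.2.6 and 6.1.1.3.2.6 on who has these visits.
4. Align footnote 2 with that frequency. A month-4 stopper without progression would then give about 8 assessments by month 24 (2 on treatment, 1 post-stop, about 5 at MRI visits). Existing contacts cannot deliver 13.
5. Optionally, collect the EORTC forms at the 3-monthly follow-up contact, with footnote 5 amended, only from patients able to complete them. Section 5.5 limits the representative to survival items.
6. State in section 10.2.1 how post-stop scores, deaths and missing forms are handled.

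The cost is amendment wording and questionnaires at visits that already take place, with some burden on ill patients and some missing forms. No treatment rule changes. The missing control scores need their own solution.

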6.1.1.3 Disease Progression

The following will be considered disease progression for determination of PFS using the updated response assessment criteria for high-grade gliomas: Response Assessment in Neuro-Oncology (RANO) working group guideline [79].

This study will apply the RANO criteria for high grade gliomas to assess radiographic disease status. These criteria specify assessment of enhancing disease to define progression and response. It is likely that a significant number of subjects eligible for the proposed study will have non-enhancing disease. For subjects without enhancing disease to be eligible for the study, the RANO allowance for FLAIR will be utilized for non-enhancing disease. FLAIR considerations are detailed in the tables below.

6.1.1.3.1 CRITERIA FOR DETERMINING FIRST PROGRESSION DEPENDING ON TIME FROM INITIAL CHEMORADIOTHERAPY

TABLE 3. RANO CRITERIA FOR DETERMINING FIRST PROGRESSION

First Progression	Definition
Progressive disease <12 weeks after completion of chemoradiotherapy	Progression can only be defined using diagnostic imaging if there is new enhancement outside of the radiation field (beyond the high-dose region or 80% isodose line) or if there is unequivocal evidence of viable tumor on histopathologic sampling (e.g., solid tumor areas [i.e., > 70% tumor cell nuclei in areas], high or progressive increase in MIB-1 proliferation index compared with prior biopsy, or evidence for histologic progression or increased anaplasia in tumor). Note: Given the difficulty of differentiating true progression from pseudoprogression, clinical decline alone, in the absence of radiographic or histologic confirmation of progression, will not be sufficient for definition of progressive disease in the first 12 weeks after completion of concurrent chemoradiotherapy.
Progressive disease ≥ 12 weeks after chemoradiotherapy completion	
 1. New contrast-enhancing lesion outside of radiation field on decreasing, stable, or increasing doses of corticosteroids. 2. Increase by ≥ 25% in the sum of the products of perpendicular diameters between the first post-radiotherapy scan, or a subsequent scan with smaller tumor size, and the scan at 12 weeks or later on stable or increasing doses of corticosteroids. 3. Clinical deterioration not attributable to concurrent medication or comorbid conditions is sufficient to declare progression on current treatment but not for entry onto a clinical trial for recurrence. 4. For patients receiving antiangiogenic therapy, significant increase in T2/FLAIR non-enhancing lesion may also be considered progressive disease. The increased T2/FLAIR must have occurred with the patient on stable or increasing doses of corticosteroids compared with baseline scan or best response after initiation of therapy and not be a result of comorbid events (e.g., effects of radiation therapy, demyelination, ischemic injury, infection, seizures, postoperative changes, or other treatment effects).

6.1.1.3.1.1 CRITERIA FOR RESPONSE ASSESSMENT INCORPORATING MRI AND CLINICAL FACTORS

Criteria for Response Assessment Incorporating MRI and Clinical Factors (Adapted from JCO 2010)

TABLE 4. RESPONSE EVALUATION AFTER A COMPLETE RESECTION

Response	Criteria
Complete response	
 Requires all of the following: complete disappearance of all enhancing measurable and non-measurable disease sustained for at least 4 weeks. No new lesions; stable or improved non-enhancing (T2/FLAIR) lesions. Patients must be off corticosteroids (or on physiologic replacement doses only) and stable or improved clinically. Note: Patients with non-measurable disease only cannot have a complete response; the best response possible is stable disease.
Partial response	
Requires all of the following:
 
 ≥ 50% decrease compared with baseline in the sum of products of perpendicular diameters of all measurable enhancing lesions sustained for at least 4 weeks. No progression of non-measurable disease. Stable or improved non-enhancing (T2/FLAIR) lesions on same or lower dose of corticosteroids compared with baseline scan; the corticosteroid dose at the time of the scan evaluation should be no greater than the dose at time of baseline scan. Stable or improved clinically. Note: Patients with non-measurable disease only cannot have a partial response; the best response possible is stable disease.
Stable disease	
Requires all of the following:
 
 Does not qualify for complete response, partial response, or progression. Stable non-enhancing (T2/FLAIR) lesions on same or lower dose of corticosteroids compared with baseline scan. In the event that the corticosteroid dose was increased for new symptoms and signs without confirmation of disease progression on neuroimaging, and subsequent follow-up imaging shows that this increase in corticosteroids was required because of disease progression, the last scan considered to show stable disease will be the scan obtained when the corticosteroid dose was equivalent to the baseline dose.
Progression	
Defined by any of the following:
 
 ≥ 25% increase in sum of the products of perpendicular diameters of enhancing lesions compared with the smallest tumor measurement obtained either at baseline (if no decrease) or best response, on stable or increasing doses of corticosteroids*. The absolute increase in any dimension must be at least 5mm when calculating the products. Significant increase in T2/FLAIR non-enhancing lesion on stable or increasing doses of corticosteroids compared with baseline scan or best response after initiation of therapy* not caused by comorbid events (e.g. radiation therapy, demyelination, ischemic injury, infection, seizures, postoperative changes, or other treatment effects). Any new measureable lesion. Clear clinical deterioration not attributable to other causes apart from the tumor (e.g. seizures, medication adverse effects, complications of therapy, cerebrovascular events, infection, and so on) or changes in corticosteroid dose. Failure to return for evaluation as a result of death or deteriorating condition; or clear progression of non-measurable disease.

- All measurable and non-measurable lesions must be assessed using the same techniques as at baseline.

- Abbreviations: MRI, magnetic resonance imaging; FLAIR, fluid-attenuated inversion recovery.
- Stable doses of corticosteroids include patients not on corticosteroids.

The determination of whether to stop treatment due to progression will be based on the investigator's evaluation of the patient's clinical condition. TTFelds treatment will be continued for 24 months or until second progression whichever occurs first unless the patient's clinical condition prohibits this. In the case of radiological progression based on local evaluation, temozolomide treatment will be stopped and a second line treatment chosen instead. The following treatments or any combination of these treatments are considered second line therapy in this protocol:

- Re-operation
- Local radiation therapy
- Second line therapy
- Combination of the above

6.1.1.3.1.2 DISEASE PARAMETERS

Measurable disease: Bi-dimensionally measurable lesions with clearly defined margins by MRI scan. All tumor measurements must be recorded in millimeters (or decimal fractions of centimeters).

Non-measurable or evaluable disease: Uni-dimensionally measurable lesions or lesions with margins not clearly defined such as areas of T2/FLAIR signal abnormality or poorly defined enhancing abnormality.

Note: For cystic lesions, the only measurable part is any enhancement area around the cyst that is clearly defined and bi-dimensionally measurable. The cyst itself should not be considered measurable or non-measurable disease.

Target lesions: All measurable lesions that are seen at baseline MRI. Target lesions should be selected on the basis of their size (lesions with the longest diameter), but in addition should be those that lend themselves to reproducible repeated measurements. It may be the case that, on occasion, the largest lesion does not lend itself to reproducible measurement in which circumstance the next largest lesion, which can be measured reproducibly should be selected. When there are too many measurable lesions, choose the largest 3 lesions as target lesions to follow. The other measurable lesions should be considered evaluable for the purpose of objective status determination.

Non-target lesions: All non-measurable lesions should be identified as non-target lesions and should also be recorded at baseline. Measurements of these lesions are not required, but the presence, absence, or in rare cases unequivocal progression of each should be noted throughout follow-up.

6.1.1.3.1.3 METHODS FOR EVALUATION OF MEASURABLE DISEASE

All measurements should be taken and recorded in metric notation using a ruler. All baseline MRI evaluations should be performed as closely as possible to Study Day 0. An MRI should be collected and evaluated after any surgical procedure (surgical resection/debulking) but not biopsy.

Clinical lesions: Clinical lesions will only be considered measurable on brain MRI when they are ≥ 10 mm (1 cm) in 2 perpendicular measurements in each of 2 perpendicular planes (i.e., axial and coronal) as assessed using a ruler.

Histology: This technique can be used to differentiate between partial responses (PR) and complete responses (CR) in rare cases when biopsy or surgical resection of a measurable lesion is clinically indicated.

Perfusion/CBV: This advanced brain MRI technique can be used as an adjunct test to determine treatment response or disease status. However, it should not be used as the primary or sole method to determine response or disease status.

Brain FDG-PET coupled with head CT or brain MRI and brain spectroscopy: These advanced metabolic imaging techniques can be used as an adjunct test to determine response or disease status. However, they should not be used as the primary or sole method of determining response or disease status.

6.1.1.3.1.4 EVALUATION OF TARGET LESIONS

Complete Response (CR): Disappearance of all target lesions.

Partial Response (PR): $\geq 50\%$ decrease compared with baseline in the sum of products of perpendicular diameters of all target lesions sustained for at least 4 weeks.

Progressive Disease (PD): At least a 25% increase in the sum of products of perpendicular diameters of at least 1 target lesion, taking as reference the smallest sum of products of perpendicular diameters on study (this includes the baseline sum if that is the smallest on study). The absolute increase in any dimension must be at least 5mm when calculating the products of perpendicular diameters.

Stable Disease (SD): Neither sufficient shrinkage to qualify for PR nor sufficient increase to qualify for PD, taking as reference the smallest sum of products of perpendicular diameters while on study.

6.1.1.3.1.5 EVALUATION OF NON-TARGET LESIONS

Complete Response (CR): Disappearance of all non-target lesions.

Non-CR/Non-PD: Persistence of one or more non-target lesion(s).

Progressive Disease (PD): Appearance of one or more new lesions and/or unequivocal progression of existing non-target lesions on stable or increasing doses of corticosteroids compared with baseline scan or best response after initiation of therapy* not caused by comorbid events (e.g. Radiation therapy, demyelination, ischemic injury, infection, seizures, postoperative changes, or other treatment effects). Unequivocal progression should not normally trump target lesion status. It must be representative of overall disease status change, not a single lesion increase.

Although a clear progression of “non-target” lesions only is exceptional, the opinion of the treating physician should prevail in such circumstances, and the progression status should be confirmed at a later time by the Study Chair.

6.1.1.3.1.6 EVALUATION OF BEST OVERALL RESPONSE

The best overall response is the best response recorded from the start of the treatment until disease progression/recurrence (taking as reference for progressive disease the smallest measurements recorded since the treatment started). The patient's best response assignment will depend on the achievement of both measurement and confirmation criteria.

TABLE 5. SUMMARY OF THE RANO RESPONSE CRITERIA (ADAPTED FROM JCO 2010)

Criterion	CR	PR	SD	PD
T1 gadolinium enhancing disease	None	$\geq 50\%$ ↓	$< 50\%$ ↓ but $< 25\%$ ↑	$\geq 25\%$ ↑*
T2/FLAIR	Stable or ↓	Stable or ↓	Stable or ↓	↑*
New lesion	None	None	None	Present*
Corticosteroids	None	Stable or ↓	Stable or ↓	NA [†]
Clinical status	Stable or ↑	Stable or ↑	Stable or ↑	↓*
Requirement for response	All	All	All	Any*

Abbreviations: RANO, Response Assessment in Neuro-Oncology; CR, complete response; PR, partial response; SD, stable disease; PD, progressive disease; FLAIR, fluid-attenuated inversion recovery; NA, not applicable.

* Progression occurs when this criterion is present.

† Increase in corticosteroids alone will not be taken into account in determining progression in the absence of persistent clinical deterioration.

NOTE: Patients may continue on treatment and remain under close observation and evaluation at 4-8 week intervals if there is uncertainty regarding whether pseudoprogression may be present as determined by the investigators. If subsequent radiographic or clinical assessments suggest that the patient is in fact experiencing progression, then the date of progression should be the time point at which this issue was first raised. Similarly, stable disease may be assigned in cases of presumed “pseudoprogression” associated with decreased steroid use.

6.1.1.3.1.7 DURATION OF RESPONSE

Duration of overall response: The duration of overall response is measured from the time measurement criteria are met for CR or PR (whichever is first recorded) until the first date that recurrent or progressive disease is objectively documented (taking as reference for progressive disease the smallest measurements recorded since the treatment started).

The duration of overall CR is measured from the time measurement criteria are first met for CR until the first date that progressive disease is objectively documented.

Duration of stable disease: Stable disease is measured from the start of the treatment until the criteria for progression are met, taking as reference the smallest measurements recorded since the treatment started, including the baseline measurements.

6.1.1.3.1.8 NEUROLOGICAL EXAM AND PERFORMANCE STATUS

Patients will be graded using the Karnofsky Performance Status scale and their neurological function evaluated as improved, stable or deteriorated in addition to objective measurement of tumor size. These parameters will be used to determine the overall response assessment.

The *Karnofsky Scale* has been adapted for use in many areas, including hospices, cancer clinics, etc., as well as used by various CFS researchers and physicians ([name]; [name]).

The 10-point scale is a quick and easy way to indicate how you are feeling on a given day, without going through several multiple-choice questions or symptom surveys.

TABLE 6: KARNOFSKY SCALE

100	Able to work. Normal; No complaints; No evidence of disease.
90	Able to work. Able to carry on normal activity; Minor symptoms.
80	Able to work. Normal activity with effort; Some symptoms.
70	Independent; not able to work. Cares for self; Unable to carry on normal activity.
60	Disabled; dependent. Requires occasional assistance; cares for most needs.
50	Moderately disabled; dependent. Requires considerable assistance and frequent care.

40	Severely disabled; dependent. Requires special care and assistance.
30	Severely disabled. Hospitalized, death not imminent.
20	Very sick. Active supportive treatment needed.
10	Moribund. Fatal processes are rapidly progressing.

6.1.1.3.1.9 PROGRESSION-FREE SURVIVAL

PFS is defined as the duration of time from start of adjuvant treatment (TMZ C1D1) to time of progression or death, whichever occurs first.

